2.3. Outcome measures/endpoints

Feasibility and feasibility measurement

As this is a feasibility study the primary outcomes of interest relate to aspects of feasibility and acceptability. A red, amber, green (RAG) system will be used to identify if the feasibility study should progress to a definitive trial. Section 7.3 Statistical Analysis Plan specifies the RAG system in more detail. The aspects of feasibility and acceptability that will be explored are:

STIM-STROKE Protocol v1.0 30-04-2025

IRAS ID: 332116 Page **18** of **70**

- 1. Interviews with people with stroke and their caregivers as well as focus groups with clinicians to explore their experiences and views about the acceptability of the SNMES intervention. Furthermore exploring/tracking adverse events and adverse reactions to treatment with SNMES (a common side effect of electrical stimulation is skin irritation from the electrode pads) will contribute to the determining the feasibility and acceptability of the intervention.
- 2. Study enrolment rates and screening (the number of patients who agree to take part of those eligible). Where possible reasons for not taking part will be recorded to help plan the definitive trial. Additionally. data will be collected on the time duration between hospital admission and randomisation.
- 3. Through a participant diary, records within the electrical stimulation machine, and participant/caregiver interviews we will estimate engagement with the protocol and explore reasons for low or non-engagement with the protocol/not achieving recommended dose. This will help the team to identify if the suggested dose is feasible and acceptable on a larger scale.
- 4. Through participant/caregiver interviews, therapist focus groups, and completeness of collected data explore the feasibility and acceptability of the outcome measures used. Acceptability of candidate outcomes measures and their variability to inform the selection of outcomes, including the primary outcome, for a definitive trial, likely to be the 10-Metre Walk Test.
- 5. The data collected (including those from the outcome measures and participant interviews, data completeness, and standard deviation estimates) will inform the sample size considerations and primary outcome measure for the definitive trial.

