4.1. Inclusion Criteria

The inclusion criteria for the participants with stroke are:

- 1. Adults ≥ 18 years of age within two-weeks of diagnosis of acute stroke
- 2. Sufficiently medically stable to participate in rehabilitation/trial interventions
- 3. National Institutes of Health Stroke Scale (NIHSS) score of ≥ 3 for the lower limb (limb weakness)
- 4. Unable to walk or transfer independently (with/without a walking aid)

Inclusion criteria for caregivers to people with stroke

1. Caregiver or family member to participant with stroke this is defined as:

An informal caregiver (hereafter referred to as caregivers) who is a family member or a close friend in a good relationship with the person with stroke. The caregiver will be older than 18 years of age, and able to communicate and assist the stroke survivor.

2. Participant with stroke they support was in the intervention group (SNMES)

STIM-STROKE Protocol v1.0 30-04-2025

IRAS ID: 332116 Page **23** of **70**

3. Caregiver or family member has the communication skills to be able to participate in an interview

Inclusion criteria for clinicians

- 1. Health care worker (e.g. but not limited to physiotherapist, occupational therapist, therapy technician/aid, nurse, healthcare assistant)
- 2. Supported the participants with stroke to use the SNMES during the study period

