All participants will complete follow up assessments at 6-weeks (Visit 2), 12-weeks (Visit 3) and 6 months (Visit 4) after randomisation. These assessments will be administered by research practitioners and take place at the trust in which the participant was admitted for their stroke (UDH or the second site). If the participant is not able to walk or completes transfers by hoist the assessment can be carried out in the community at their place of residence. Research team members that undertake assessments in the participant's place of residence and will follow lone working policies associated with the trust.

Follow up Assessments

A summary of the study baseline and follow up assessments are in Section 5.5 and 5.6 as well as in Table 2 in Section 5.6.

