Limb circumference	This is to assess muscle bulk and track potential muscle atrophy (muscle wasting) through measuring the circumference of thigh and calf with a tape measure.		Х	X	×	Х
EQ-5D-5L	Assessment of health-related quality of life.		Х	Х	Х	Х

Measure	Brief Description	Screening	Visit 1 (baseline)	Visit 2 (6- weeks) (+/- 3 days)	Visit 3 (12 - weeks) (+/- 7 days)	Visit 4 (6 months) (+/- 7 days)
Barthel Index	Assesses the ability to perform everyday activities e.g. dressing, bathing, walking, toileting.		Х	Х	X	Х
Nottingham Sensory Assessment – Tactile Sensation Subsection	Assesses the participants sensation to light touch on the lower limbs.		X	X	×	X
10 Metre Walk Test	Assesses walking ability and function. Measurement of the time it takes to walk 10 meters (with or without an assistive device).		(not completed due to inclusion criteria not being able to walk)	(not completed due to inclusion criteria not being able to walk)	X	X
Resource use Questionnaire	Health resources and therapy accessed (e.g. travel costs to appointments, number and length of healthcare visits, support at home) over the course of the study.			X	×	X

Measure	Brief Description	Screening	Visit 1 (baseline)	Visit 2 (6- weeks) (+/- 3 days)	Visit 3 (12 - weeks) (+/- 7 days)	Visit 4 (6 months) (+/- 7 days)
Semi- structured Interview participants with stroke and their caregivers.	Interviews with participants and their caregivers to explore their experience of the research, using SNMES, and their acceptability of SNMES. There will be n=12 participants interviewed from the intervention group, n=8 from the control group, and n=10 caregivers to the person with stroke in the intervention group.				X (convenience sample of participants with strokes will be interviewed) And (convivence sample of caregivers to participants with stroke receiving SNMES will be interviewed)	
Clinician Focus Group	Focus group with clinicians (n=10) will explore their perspectives on the feasibility and acceptability of the intervention and research processes.					X (convivence sample of clinicians supporting the intervention will take part in a focus group; at

STIM-STROKE Protocol v1.0 30-04-2025

IRAS ID: 332116 Page **43** of **70**

Measure	Brief Description	Screening	Visit 1 (baseline)	Visit 2 (6- weeks)	Visit 3 (12 - weeks)	Visit 4 (6 months)
				(+/- 3 days)	(+/- 7 days)	(+/- 7 days)
						the end of the intervention period)

Page **44** of **70**

IRAS ID: 332116

Modified Rankin Score

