Sensation in the lower limbs will be assessed using the Nottingham Sensory Assessment, Tactile Sensation subscale. There is demonstrated reliability of the tactile subsection in people with intracranial disorders. ³⁶

STIM-STROKE Protocol v1.0 30-04-2025

IRAS ID: 332116 Page **45** of **70**

EuroQol – 5 Dimensions-5 Levels

EQ-5D-5L (EuroQol) is a patient-reported quality of life measure evaluating 5 domains mobility, self-care, usual activities, anxiety/depression, pain/discomfort. The EQ-5D-5L has demonstrated good reliability (k between 0.63- 0.80)34 responsiveness, and minimal clinically important difference in people following stroke. The EQ-5D-5L is available both in paper format and an online format.

For participants who have changes to cognition or communication who are not able to complete the EQ-5D-5L proxy completion will be used. The proxy completion will be by a family member, caregiver, or significant other who can report on the person's function and quality of life. Proxy report for people with stroke demonstrates greater agreement for more observable questions e.g. mobility and self-care as well as greater agreement 6 months after stroke versus within 2-3 weeks after stroke.³⁹

Barthel Index

The Barthel Index is a patient-reported measure of function and activities of daily living. The Barthel Index has 10 items/questions around activities of daily living including: feeding, bathing, grooming, dressing, bowel control, bladder control, toileting, chair transfer, ambulation and stair climbing. Each item is rated from 0 dependent, 5 needs some assistance, to 10 independent. The Barthel Index has demonstrated good reliability and validity in people following stroke.^{40,41}

10-Metre Walk Test

The 10-Metre Walk Test is a measure of functional ability in which an individual is timed walking at a comfortable speed for 10 metres. When used in people after stroke, the 10-metre walk test is reliable (ICC=0.83) and has demonstrated minimal detectable change. If this study progresses to a definitive trial the 10 Metre Walk Test will be the primary outcome measure.

Resource Use Questionnaire

The resource use questionnaire will track the participants use of health care services such as number of physiotherapy or occupational therapy appointments, nurse appointments, GP appointments, any support at home from a carer, support for cooking and clearing at home, and costs to travel to appointments etc.

Semi-structured interview

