7.3. Statistical analysis plan

Quantitative data

A detailed statistical analysis plan (SAP) will be drafted by the trial statistician and the trial will be reported in accordance with the CONSORT 2010 statement extension to pilot and feasibility trials.⁴⁸

STIM-STROKE Protocol v1.0 30-04-2025

IRAS ID: 332116 Page **54** of **70**

No statistical comparisons between treatment groups will be undertaken on baseline or follow-up data as the trial is not designed to test effectiveness. Iinstead the focus will be on presenting summary statistics with appropriate confidence intervals, to meet listed study objectives.

The flow of participants through the study will be presented in a CONSORT-style diagram with reasons for discontinuation or withdrawal given where available. Descriptive statistics will be reported for the feasibility outcomes: recruitment, retention rate, adherence rates, quality of data collection, intervention delivery and fidelity. Additionally, descriptive statistics will be used to describe the outcome measures collected at Visits 1-4.

Data will inform a potential definitive study with variability in candidate primary and secondary measures calculated to inform size (power calculation) for the definitive trial.

Adverse events will be summarised descriptively.

Data management will be undertaken using REDCap and Microsoft Excel. Statistical analysis will be undertaken using STATA version 16 or later, supplemented where required by R.

Qualitative and quantitative data will be used in combination to inform the future definitive trial design. The intervention and methodology will also be iteratively mapped to the TIDieR checklist, APPEASE framework and Health Inequalities Assessment toolkit.

Qualitative data

Interviews/focus groups will be recorded and transcribed verbatim using an approved transcription service that complies with GDPR. All identifying features of the recording and transcription will be anonymised.

Thematic analysis using the framework method will be used to explore common themes taking a deductive approach and considering emergent themes involving inter-researcher and PPI interpretation ^{44,49} Data management and data analysis may be undertaken using NVivo software.

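### The 10 Metre Walk Test, leading candidate primary outcome, is defined only as a time, so participants still unable to walk have no value and its SD would describe recovered walkers

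*Protocol*

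**What the plan says.** Inclusion criterion 4 (Protocol 4.1) admits people who are "Unable to walk or transfer independently (with/without a walking aid". Table 2 in section 5.6 describes the walk test as "Measurement of the time it takes to walk 10 meters (with or without an assistive device", and the text below the table says that "an individual is timed walking at a comfortable speed for 10 metres". The test is scheduled at Visit 3 (12 weeks) and Visit 4 (6 months). At Visits 1 and 2 the table marks it as "not completed due to inclusion criteria not being able to walk".

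The protocol expects some participants still not to walk later on. Section 5 says of the follow-up visits: "If the participant is not able to walk or completes transfers by hoist the assessment can be carried out in the community".

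On the role of the measure, section 5.6 is firm: "If this study progresses to a definitive trial the 10 Metre Walk Test will be the primary outcome measure". Section 2.3 and the trial summary are softer; section 2.3 has "likely to be the 10-Metre Walk Test" and makes the acceptability and variability of candidate measures the basis for choosing. Section 7.3 plans to have "variability in candidate primary and secondary measures calculated to inform size (power calculation) for the definitive trial". Section 7.3.2 plans descriptive statistics for the test and gives no rule for a participant who cannot do it. Section 7.1 bases the sample of 60 partly on SD precision for numerical scales: an inflation factor of 1.1 at more than 80% one-sided confidence.

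**The concern.** A person who cannot walk 10 m has no time. No missing-data method supplies one, because the quantity does not exist for that person. If only times are summarised, the mean and SD are conditional on regaining walking, which happens after randomisation and which the intervention is meant to influence. The definitive trial will randomise people who cannot walk independently, so an SD from recovered walkers is the wrong input to its sample size.

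Two further things are at stake. The SD precision in section 7.1 assumes about 60 values, and this measure will have fewer. Also, if inability leaves a blank field, it cannot be told apart from a missed test, which blurs the completeness data that section 2.3 wants for choosing the outcome.

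**Working it through.** **1. What a non-walker receives under the text.** The measure is a time (Table 2 and the section 5.6 text). The protocol's only explicit handling of inability is at Visits 1 and 2, where the test is marked as not completed. For Visits 3 and 4 nothing shown assigns a score, converts time to speed, or separates inability from missing data. Following the text therefore yields values for walkers only.

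**2. The protocol's own precision figure.** The one-sided 80% upper limit for an SD is the estimate multiplied by

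factor = √(df / χ²(0.20, df)), with df = n − 2 (SD pooled over two arms).

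The confidence attached to a factor of 1.1 is P(χ²(df) > df / 1.21).

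- n = 60: df = 58, χ²(0.20, 58) = 48.80, factor = √(58/48.80) = 1.090. Confidence at 1.1 is 82.4%. The section 7.1 claim is reproduced.
- The smallest df that keeps the factor within 1.1 is 49, which means 51 measured values with two arms pooled (50 as a single sample).

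**3. The same calculation with walkers only.** The documents give no share regaining the ability to walk 10 m, so 30%, 50% and 70% are assumptions. The 20% loss is the green/amber boundary for incomplete 6-month follow-up in Table 3: 60 × 0.80 = 48. Factor² − 1 is the extra sample size if the upper limit is used for planning.

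| Follow-up | Who has a value | n | Factor | Factor² − 1 | Confidence at 1.1 |
|---|---|---|---|---|---|
| No loss | all | 60 | 1.090 | 19% | 82.4% |
| No loss | 70% walk | 42 | 1.112 | 24% | 77.4% |
| No loss | 50% walk | 30 | 1.139 | 30% | 72.6% |
| No loss | 30% walk | 18 | 1.198 | 44% | 65.6% |
| 20% lost | all | 48 | 1.103 | 22% | 79.3% |
| 20% lost | 70% walk | 34 | 1.128 | 27% | 74.4% |
| 20% lost | 50% walk | 24 | 1.161 | 35% | 69.5% |
| 20% lost | 30% walk | 14 | 1.240 | 54% | 62.3% |

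The effect of non-walking is read within a follow-up block: 1.090 to 1.11–1.20 with no loss, or 1.103 to 1.13–1.24 with 20% lost. The step from 1.090 to 1.103 is attrition alone.

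**4. The population problem, apart from precision.** For illustration only, assume walkers have mean speed 0.6 m/s and SD 0.3 m/s, and score those unable as 0. With share w walking, the variance over everyone is w(0.3² + 0.6²) − (0.6w)².

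- w = 0.3: 0.1350 − 0.0324 = 0.1026, SD 0.32
- w = 0.5: 0.2250 − 0.0900 = 0.1350, SD 0.37
- w = 0.7: 0.3150 − 0.1764 = 0.1386, SD 0.37

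Against the walkers' variance of 0.09, the variance ratios are 1.14, 1.50 and 1.54. For the same absolute difference, a sample size built on the walkers' SD would be too small by those factors. Other assumed speeds would give other ratios; the point is that the two SDs are different quantities.

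**The case against.** The strongest reply is that this is inferred from silence. Table 2 offers only a brief description, full test instructions are referred to Appendix 3, and a detailed SAP is still to be drafted. Either could hold a scoring rule, and neither is shown. That stands as a limit on certainty. It does not remove the point, because the protocol body fixes the measure as a time and rests its precision on 60 values.

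Second, the proposed analysis may be largely recoverable. Speed is 10 m divided by time, and the Barthel Index, with an ambulation item, is collected at every visit. This is partly right, but the Barthel item is coarse and does not record whether someone attempted the walk test and could not complete 10 m.

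Third, finding out whether the test suits this population is the study's purpose, and progression rests on recruitment, retention and adherence, not on this SD. That lowers the severity. It also strengthens the case for recording inability explicitly, since that is what the study needs to learn.

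Fourth, the test allows an assistive device, so not walking independently is not the same as having no time. This is correct, and it is one reason the share without a time can only be given as a range.

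Some stronger readings are tempting but unsupported. A reader might infer that the protocol prescribes a walkers-only analysis; it does not say so. A reader might infer that a walkers-only mean would make SNMES look worse in this trial. That can be constructed from assumed inputs, but section 7.3 rules out statistical comparisons between groups. A reader might also infer that non-walkers will be counted as incomplete in Table 3. That criterion concerns follow-up at 6 months and does not mention walk times, and section 5 allows assessment at home for non-walkers.

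**Conclusion.** The point holds, and it should be fixed. As the protocol stands, its leading candidate primary outcome has no value for participants who cannot walk 10 m at Visits 3 and 4. The resulting mean and SD would describe those who regained walking, not the population for which the definitive trial is to be sized.

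The 1.1 factor at over 80% confidence is correct for 60 values but would not hold for this measure at any assumed walking share from 30% to 70%. At the 70% end the loss of precision is small (27% against 22% with attrition); at the 30% end it is substantial (54% against 22%). The change of population matters whatever the share, provided some participants remain unable to walk.

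The conclusion assumes that neither Appendix 3 nor the SAP contains a rule for non-walkers. It does not put the feasibility aims or the progression decision at risk, so it falls short of a fault that must be cured for the study to be valid. The firm and softer statements about the primary outcome are a separate, smaller inconsistency.

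**What to change.** 1. On the CRF at Visits 3 and 4, add a category for assessed but unable to walk 10 m, distinct from missing and from death. Count it as a completed assessment, and say so wherever completeness is defined.
2. Express the result as walking speed (10 m divided by time).
3. At each of these visits report, by arm, the proportion able to walk 10 m and the mean and SD of speed over all assessed participants, with 0 m/s for those unable. Give the walkers-only summary alongside and report deaths separately.
4. Base the definitive sample size on a summary that covers all assessed participants. Speed with zeros is one workable choice; the proportion walking, or a two-part or rank-based summary, would also meet the requirement.
5. Reconcile the firm wording in section 5.6 with the softer wording in section 2.3 and the trial summary, for example by calling the test the leading candidate throughout.
6. If Appendix 3 or the SAP already has a rule for non-walkers, state it in section 5.6.

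The cost is a few sentences and one tick box. The downside is a distribution with many zeros, for which normal-theory limits on the SD, including the factors above, are only approximate. The definitive trial would face that distribution anyway, so it is useful to see it here.

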5.7. Long term follow-up assessments

The intervention period is 12 weeks. Participants will have an assessment at the end of the follow up period, Visit 3 at 12-weeks, and one follow-up assessment after the end of the intervention period, this is Visit 4 and is 6 months after randomisation. The table below outlines the assessments that will be undertaken at Visit 4 and the rationale. Please refer to the previous section 5.6 Trial Assessments and Table 2 for details and rationale for each assessment, and Appendix 3 for details of how to carry out each assessment.

5.8. Qualitative assessments

Participants with Stroke

A subgroup of participants from the intervention group (n=12) and control group (n=8) will take part in a semi-structured interview which will be offered online, in-person or over the phone depending on the participant preference. The process of recruitment is in section 5.1. Interviews will be audio recorded for transcription. The interviews will be between 30-45 minutes and will take place after completing the 12-week intervention. The interviews will be conducted by a member of the research team who has experience in and has been trained in interviews and is on the delegation log, they will be supported by the team.

The sample size in the nested qualitative component (n=20) will be adequate to reach data saturation based on recent research around code and meaning saturation in qualitative research.⁴³

A convenience sample of participants will be sought to take part in the interviews. The convenience sample will be representative of the participants with stroke recruited to the trial e.g. functional level, other associated impairments. Participants with communication difficulties will be supported to take part; their views and experiences are important and valued.

Participants with stroke interviews will explore their experiences of the study, recruitment, randomisation, data collection methods, acceptability of taking part in the research, and suggestions for future improvement. Participants from the SNMES group will further explore the recommended SNMES protocol, engagement with the SNMES sessions, ease of using the leg brace, ease of using the stimulator and suggestions for future improvement. The interview topic guide will be informed by the Theoretical Framework of Acceptability.⁴⁴ The

STIM-STROKE Protocol v1.0 30-04-2025

IRAS ID: 332116 Page **47** of **70**

topic guide will also be developed with input from the public advisory group (PAG) input and will be iteratively refined during the interviews.

Clinician Participants

A convenience sample of clinicians(e.g. therapists, nurses, health care assistants) who have supported the participants with stroke to carry out the SNMES intervention will be invited to take part in a focus group. Please see above Section: Screening, Identification, and Recruitment above for details on the identification and recruitment process.

Focus groups (n=2) will include between 4-5 clinicians, take place at the trust they are working in, or online depending on the group preference and will last around 45 minutes. Focus groups will be audio recorded for transcription. Focus groups have the advantage of social interaction between participants and allow for consensus or debate around a topic providing rich meaningful data to help to develop the SNMES intervention and future research methods. The focus group will be conducted by a member of the research team who has experience in and has been trained in interviews (qualitative methods) and is on the delegation log, they will be supported by the team.

The clinician focus groups will explore recruitment methods, ease of using the stimulator, ease of donning and doffing the knee and ankle brace, participant adherence from their perspective (barriers and facilitators), study methods, and their thoughts and attitudes. attitudes towards the intervention. If the intervention is successful, the goal would be adoption into practice. The interview topic guide will be informed by the Theoretical Framework of Acceptability.⁴⁴ The topic guide will also be developed with input from the public advisory group (PAG) input and will be iteratively refined during the interviews.

Caregiver Participants

A convenience sample of caregivers/family members who supported the participants with stroke to use the SNMES will be invited to take part in a semi-structured interview. To understand a range of experiences the team will aim to purposively sample caregivers to participants with stroke with a range of functional abilities and impairments.

Interviews will be offered online, in-person or over the phone depending on the caregiver participant preference. Interviews will be audio recorded for transcription at a later date. The interviews will be between 30-45 minutes and will take place after the participant with stroke has completed the 12-week intervention period. The interviews will be conducted by a member of the research team who has experience in and has been trained in interviews (qualitative methods) and is on the delegation log, they will be supported by the team.

Caregiver participant interviews will explore their experiences of the study, supporting the person with stroke to use the SNMES, the ease of using the SNMES and braces if used, data collection methods, any perceived barriers or facilitators to using the SNMES and suggestions for future improvement in the research and SNMES intervention. The interview topic guide will be informed by the Theoretical Framework of Acceptability.⁴¹ The topic guide will also be developed with input from the public advisory group (PAG) input and will be iteratively refined during the interviews.

Data from all interviews and focus groups will help to inform design aspects related to participant, caregiver, and therapist involvement in the next phase of the research as well as to develop robust methodology.

STIM-STROKE Protocol v1.0 30-04-2025

IRAS ID: 332116 Page **48** of **70**

